8.1.2 Serious Adverse Event Definition

Serious AE (SAE) means any untoward medical occurrence that at any dose:

- Results in **death**.

- Is **life-threatening** (refers to an AE in which the patient was at risk of death at the time of the event. It does not refer to an event which hypothetically might have caused death if it were more severe).
- Requires inpatient **hospitalization or prolongation of an existing hospitalization** (see clarification in the paragraph below on planned hospitalizations).
- Results in **persistent or significant disability or incapacity**. (Disability is defined as a substantial disruption of a person's ability to conduct normal life functions).
- Is a **congenital anomaly/birth defect**.
- Is a **medically important event (Tables 4-2 and 4-3)**. This refers to an AE that may not result in death, be immediately life threatening, or require hospitalization, but may be considered serious when, based on appropriate medical judgment, may jeopardize the patient, require medical or surgical intervention to prevent 1 of the outcomes listed above, or involves suspected transmission via a medicinal product of an infectious agent. Examples of such medical events include allergic bronchospasm requiring intensive treatment in an emergency room or at home, grade 4 neuropathy, cardiac, or hepatic toxicity, blood dyscrasias or convulsions that do not result in inpatient hospitalization, or the development of drug dependency or drug abuse; any organism, virus, or infectious particle (eg, prion protein transmitting Transmissible Spongiform Encephalopathy), pathogenic or nonpathogenic, is considered an infectious agent.

Clarification should be made between a serious AE (SAE) and an AE that is considered severe in intensity (Grade 3 or 4), because the terms serious and severe are NOT synonymous. The general term *severe* is often used to describe the intensity (severity) of a specific event; the event itself, however, may be of relatively minor medical significance (such as a Grade 3 headache). This is NOT the same as *serious*, which is based on patient/event outcome or action criteria described above, and is usually associated with events that pose a threat to a patient's life or ability to function. A severe AE (Grade 3 or 4) does not necessarily need to be considered serious. For example, a white blood cell count of 1000/mm³ to less than 2000 is considered Grade 3 (severe) but may not be considered serious. Seriousness (not intensity) serves as a guide for defining regulatory reporting obligations.

8.2 Procedures for Reporting Serious Adverse Events

AEs may be spontaneously reported by the patient and/or in response to an open question from study personnel or revealed by observation, physical examination, or other diagnostic procedures. When possible, signs and symptoms indicating a common underlying pathology should be noted as one comprehensive event. For serious AEs, the investigator must determine both the intensity of the event and the relationship of the event to study drug administration.

AEs which are serious must be reported to Millennium Pharmacovigilance (or designee) from the first dose of study drug through 30 days after administration of the last dose of ixazomib. Any SAE that occurs at any time after completion of ixazomib treatment or after the designated follow-up period that the sponsor-investigator and/or sub-investigator considers to be related to any study drug must be reported to Millennium Pharmacovigilance (or designee). In addition, new primary malignancies that occur during the follow-up periods must be reported, regardless of causality to study regimen, up to one month after the last dose of the investigational product, starting from the first dose of study drug. All new cases of primary malignancy must be reported to Millennium Pharmacovigilance (or designee).

Planned hospital admissions or surgical procedures for an illness or disease that existed before the patient was enrolled in the trial are not to be considered AEs unless the condition deteriorated in an unexpected manner during the trial (e.g., surgery was performed earlier or later than planned). All SAEs should be monitored until they are resolved or are clearly determined to be due to a patient's stable or chronic condition or intercurrent illness(es).

Since this is an investigator-initiated study, the principal investigator [name], also referred to as the sponsor-investigator, is responsible for reporting serious adverse events (SAEs) to any regulatory agency and to the sponsor- investigator's EC or IRB.

Regardless of expectedness or causality, all SAEs (including serious pretreatment events) must also be reported in English to Millennium Pharmacovigilance (or designee):

Fatal and Life Threatening SAEs within 24 hours of the sponsor-investigator's observation or awareness of the event

All other serious (non-fatal/non life threatening) events within 4 calendar days of the sponsor-investigator's observation or awareness of the event

See below for contact information for the reporting of SAEs to Millennium Pharmacovigilance. The sponsor-investigator must fax or email the SAE Form per the timelines above. A sample of an SAE Form will be provided.

The SAE report must include at minimum:

- **Event term(s)**
- **Serious criteria**
- **Intensity of the event(s):** Sponsor-investigator's or sub-investigator's determination. Intensity for each SAE, including any lab abnormalities, will be determined by using the NCI CTCAE version specified in the protocol, as a guideline, whenever possible. The criteria are available online at <http://ctep.cancer.gov/reporting/ctc.html>.
- **Causality of the event(s):** Sponsor-investigator's or sub-investigator's determination of the relationship of the event(s) to study drug administration.

Follow-up information on the SAE may be requested by Millennium.

In the event that this is a multisite study, the sponsor-investigator is responsible to ensure that the SAE reports are sent to Millennium Pharmacovigilance (or designee) from all sites participating in the study. Sub-investigators must report all SAEs to the sponsor-investigator so that the sponsor-investigator can meet his/her foregoing reporting obligations to the required regulatory agencies and to Millennium Pharmacovigilance, unless otherwise agreed between the sponsor-investigator and sub-investigator(s).

Relationship to all study drugs for each SAE will be determined by the investigator or sub-investigator by responding yes or no to the question: Is there a reasonable possibility that the AE is associated with the study drug(s)?

Sponsor-investigator must also provide Millennium Pharmacovigilance with a copy of all communications with applicable regulatory authorities related to the study product(s), as soon as possible but no later than 4 calendar days of such communication.

SAE and Pregnancy Reporting Contact Information

US & Canada

[contact]
Email: [contact]

Rest of World
[contact]

E-mail: [contact]

Suggested Reporting Form:

- SAE Report Form (provided by Millennium)
- US FDA MedWatch 3500A:

<http://www.fda.gov/Safety/MedWatch/HowToReport/DownloadForms/default.htm>

- Any other form deemed appropriate by the sponsor-investigator

8.3 Procedures for Reporting Drug Exposure During Pregnancy and Birth Events

If a woman becomes pregnant or suspects that she is pregnant while participating in this study or within 90 days after the last dose, she must inform the investigator immediately and permanently discontinue study drug. The sponsor-investigator must immediately fax a completed Pregnancy Form to the Millennium Department of Pharmacovigilance or designee (see Section 8.2). The pregnancy must be followed for the final pregnancy outcome.

If a female partner of a male patient becomes pregnant during the male patient's participation in this study, the sponsor-investigator must also immediately fax a completed Pregnancy Form to the Millennium Department of Pharmacovigilance or designee (see Section 8.2). Every effort should be made to follow the pregnancy for the final pregnancy outcome.

Suggested Pregnancy Reporting Form:

- Pregnancy Report Form (provided by Millennium)

9. SAFETY MONITORING

9.1 Safety Monitoring

The investigator is responsible for monitoring the safety of subjects who have enrolled in the study. For this study, adverse events will be solicited from subjects to identify an occurrence or worsening of an unintended sign or symptom, related to the ingestion of the study drug. The study team will ask subjects prior to each cycle if they experienced any new medical related signs or symptoms since taking the study drug. Subjects will be asked about any adverse events they may have experienced again monthly, prior to each cycle, and at the five study visits. Only the adverse events considered related (possibly, probably or definitely) to the ingestion of the study drug will be entered into and managed in the ICTR OnCore system quarterly.

At each visit, subjects will be assessed for AEs by the study team. They will be examined by the principal investigator 5 times (please see tables 2-1 a-b and Figure 1, below): Days 1, 85, 169, 253, and 373 + 6, - 3).

- Day 1: Prior to treatment initiation. H&P, Labs, Bone Marrow Aspirate
- Day 85 + 6, - 3: Prior to treatment dose. H&P, Labs
- Day 169 + 6, - 3 Prior to treatment dose. H&P, Labs
- Day 253 + 6, - 3 Prior to treatment dose. H&P, Labs
- Day 373 + 6, - 3 After treatment completion, H&P, Labs, Bone Marrow Aspirate
- Study drug will be dispensed at each month's in-person visit, prior the initiation of the next cycle, and after reviewing the AEs and monthly labs.

- Patients will undergo monthly CBC and bi-weekly liver function tests (LFTs) for the first three months. After the first 3 months, CBCs and LFTs will be done monthly. cPRA, BAFF/APRIL, DSA and antibodies will be checked every three months (5 times total). Bone marrow aspirates will be collected at the beginning and at one of the following time points: one month (+ 6, - 3 days) after the end of the 12 month study, cPRA<80%, time of transplant, or time of subject withdrawal from the study.
- Additional visits may be required if the subject has to hold treatment and needs to return to the clinic for blood draws to confirm eligibility to continue. Please see Table 4-3, Dose Adjustments for Hematologic Toxicities for dose adjustment plan.

Based on the subject population, it is anticipated that the laboratory results that will be abstracted from the EMR for study purposes will be abnormal. The PI will not make clinically significant/non-clinically significant determinations of these results, as this subject population is expected to be abnormal and clinically significant hence their current clinical treatment. All reportable events related to the study protocol and its associated procedures will be reported to the IRB. It is the responsibility of the Investigator to promptly notify the Institutional Review Board of all unanticipated problems involving risk to human research subjects. Reportable events, such as protocol noncompliance, serious adverse events, new information, and unanticipated problems will be reported to the IRB and DMC in accordance with the UW IRB guidelines.

We will utilize the UW ICTR Data Monitoring Committee (DMC) to oversee the study. The UW ICTR DMC is comprised of experienced members (core plus ad hoc) with expertise required to oversee this study. In providing oversight for the conduct of this study, the ICTR DMC will meet annually during the five year time period in which subjects will have any study procedures. At these annual meetings, the DMC members will review protocol-specific reports created by statisticians using data pulled from the ICTR OnCore clinical research management system. These standard reports will include an overview of study objectives, a review of actual and projected accrual rates, an evaluation of patient demographics, a summary of the number and seriousness of adverse events, and an analysis of the primary and secondary outcomes. The safety data that will be reviewed includes the number and seriousness of infections, malignancies, hematological complications including leucopenia, anemia, and thrombocytopenia, cardiovascular complications and events, distal neuropathy, gastrointestinal symptoms, and immunosuppression-related adverse effects. Additional specific safety areas that will be closely monitored are listed in Section 1.10.

Source documents may be reviewed to allow the DMC to independently judge whether the overall integrity and conduct of the protocol remain acceptable based on data provided and reported by the Principal Investigator. The DMC will make recommendations to the Principal investigator that could include actions of continuation, suspension, modification or termination.

The boundary for excess harm will equal observed harm which, in the judgment of the DMC, is excessive. We will report all AEs and SAEs into OnCore for review by the DMC and the IRB oversight committee UW Madison Health Sciences IRB (HS-IRB) in accordance with the HS-IRB reporting guidelines.

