Fatigue was the most common AE reported among 384 patients treated in the oral (PO) studies (47%). Other common AEs reported in the pooled intravenous (IV) and PO safety populations include nausea, thrombocytopenia, diarrhea, and vomiting. Rash is also a commonly reported treatment-emergent event; however, there is some variety in its characterization and causality resulting in different preferred terms to describe it. A high-level term outline of rash events includes rashes, eruptions and exanthems NEC; pruritus NEC; erythemas; papulosquamous conditions; and exfoliative conditions. The dose escalation phases of most trials reported in the IB have now completed enrollment, and gastrointestinal (GI) symptoms were the common dose-limiting toxicities (DLTs) when the use of prophylactic anti-emetics was not permitted per protocol. In the expansion cohorts or phase 2 cohorts (as per each study), the incidence and severity of GI symptoms was mitigated by the use of the lower maximum tolerated dose (MTD)/recommended phase 2 dose (RP2D) (as per each study) and standard clinical usage of anti-emetics and/or antidiarrheal medications as deemed appropriate. Prophylactic use of anti-emetics has not been required as with other agents but (as outlined in Section 6.7) has been used according to standard practice and are effective.

The most frequent (at least 20%) treatment-emergent adverse events (TEAEs) reported with the PO formulation pooled from single-agent studies (n = 201) irrespective of causality to ixazomib, include nausea (53%), fatigue (51%), diarrhea (44%), thrombocytopenia (34%), vomiting (38%), decreased appetite (32%), fever (21%), and anemia (21%). The most frequent (at least 20%) TEAEs reported with the PO formulation pooled from combination trials (irrespective of the combination) (n = 173), irrespective of causality to ixazomib, include diarrhea (47%), fatigue (44%), nausea (38%), peripheral edema (35%), constipation (33%), insomnia (29%), thrombocytopenia (28%), anemia (26%), vomiting (26%), neutropenia (25%), back pain (24%), pyrexia (23%), peripheral edema (21%, each), fever (20%), cough (20%), hypokalemia (20%),

neutropenia (20%), and upper respiratory tract infection (20%). Overall rash of all grades is reported in approximately 50% of patients and is more common when ixazomib is given in combination with lenalidomide where rash is an overlapping toxicity.

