3. STUDY ENDPOINTS

3.1 Primary Endpoints (safety and efficacy)

Primary efficacy and safety endpoint:

- Efficacy endpoint: A decline in cPRA > 20%.
- Safety endpoint: infections, malignancies, hematological complications including leucopenia, anemia, and thrombocytopenia, cardiovascular complications and events, distal neuropathy, gastrointestinal symptoms, and immunosuppression-related adverse effects.

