8.1 Definitions

8.1.1 Adverse Event Definition

Adverse event (AE) means any untoward medical occurrence in a patient or subject administered a pharmaceutical product; the untoward medical occurrence does not necessarily have a causal relationship with this treatment. An AE can therefore be any unfavorable and unintended sign (including an abnormal laboratory finding), symptom, or disease temporally associated with the use of a medicinal (investigational) product whether or not it is related to the medicinal product. This includes any newly occurring event, or a previous condition that has increased in severity or frequency since the administration of study drug. AEs will be assessed at study visits and during the final follow-up study visit. In addition, data on rejection, graft, and patient survival will be collected for 6 months following kidney transplantation.

An abnormal laboratory value will not be assessed as an AE unless that value leads to discontinuation or delay in treatment, dose modification, therapeutic intervention, or is considered by the investigator to be a clinically significant change from baseline. These AEs will be entered into the OnCore system.

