9.4 DATA MANAGEMENT SYSTEM

9.4.1 Data Collection Tools

The critical data collected to address the study objectives will be electronically captured and managed in the clinical trials management software, OnCore, managed by the Institute for Clinical and Translational Research (ICTR). The study specific data collection tools will be developed and maintained with the assistance of the ICTR OnCore data management team, in consultation with the ICTR Study Monitoring Service and the ICTR Data Monitoring Committee to ensure the collection and recording all subject considered critical to answer the study objectives. It is the Investigator's responsibility to ensure that these are properly, legibly and fully completed and signed where appropriate. The data collection forms are used to record study data and are an integral part of the study and subsequent reports.

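### Section 9.1 gives two conflicting rules for entering adverse events in OnCore; following the related-only rule would drop non-serious events judged unrelated from the DMC reports

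*Combined protocol and SAP*

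**What the plan says.** Section 9.1 states the entry rule for OnCore twice. Its first paragraph says that "Only the adverse events considered related (possibly, probably or definitely) to the ingestion of the study drug will be entered into and managed" in that system. Its last paragraph says "We will report all AEs and SAEs into OnCore for review by the DMC".

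Section 8.1.1 defines an AE as an untoward occurrence "whether or not it is related to the medicinal product". It then lists when an abnormal laboratory value counts as an AE: when it leads to stopping, delay, dose change or intervention, or when the investigator judges the change from baseline clinically significant. It sends those AEs to OnCore without mentioning relatedness.

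Collection is broad. Section 9.1 also says "Subjects will be asked about any adverse events they may have experienced again monthly".

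Two uses of OnCore matter here. At annual meetings the DMC will "review protocol-specific reports created by statisticians using data pulled from the ICTR OnCore clinical research management system" (Section 9.1). Section 9.4.1 says "The critical data collected to address the study objectives will be electronically captured and managed in the clinical trials management software, OnCore".

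The primary safety endpoint in Section 3.1 begins with "infections, malignancies, hematological complications including leucopenia, anemia, and thrombocytopenia, cardiovascular complications and events" and goes on to neuropathy and gastrointestinal symptoms. Only its last category, adverse effects tied to immunosuppression, carries an attribution. Section 7.1.8 repeats the list.

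**The concern.** If the related-only sentence is applied, an event can meet the AE definition, fall in a category of the primary safety endpoint, be reported by the patient at a visit, and still never reach the database. The loss happens at entry and depends on the investigator's attribution.

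Three features of the trial make this worth correcting:

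- It is single-arm and open-label, so its safety reading rests on absolute incidence, and a shortfall in recorded events passes straight into that reading.
- Section 9.1 sets no numeric boundary for excess harm and leaves it to the DMC's judgement, which depends heavily on what has been entered.
- The ixazomib rates in Section 1.3 were "pooled from single-agent studies (n = 201) irrespective of causality to ixazomib". A related-only count would be on a different basis. The plan states no formal comparison with those rates, and they come from patients with cancer, so this affects context only.

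The meaning of the filter is also unsettled. Section 6.2 uses study drug for the ixazomib capsules, while Section 8.2 asks about the relationship to all study drugs. It is unclear whether an event attributed to dexamethasone would pass.

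**Working it through.** The plan gives no figure to reproduce on this point. The check compares texts, followed by simple arithmetic on scale.

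**Step 1: the entry statements, applied to a non-serious AE judged unrelated.**

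| Place | Scope | Relatedness filter | Entered? |
|---|---|---|---|
| Section 9.1, first paragraph | AEs | Yes, at least possibly related | No |
| Section 9.1, last paragraph | All AEs and SAEs | None | Yes |
| Section 8.1.1 | Laboratory values that qualify as AEs | None | Yes |

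The first two rows conflict for every such event, and the first and third conflict for laboratory AEs. Two of the three statements agree. The last paragraph of Section 9.1 ends with a reference to the IRB's reporting guidelines. That may limit what goes to the IRB, but it does not turn all AEs into related AEs for entry.

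**Step 2: which events are exposed.**

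- SAEs: Section 8.2 sends all of them to the manufacturer's pharmacovigilance group whatever the causality, and Section 9.1 treats them as reportable to the IRB and DMC. Under the related-only rule an unrelated SAE would still be absent from OnCore itself.
- Thrombocytopenia and gastrointestinal events: Section 8 already associates thrombocytopenia, diarrhea, nausea and vomiting with ixazomib, so they are less likely to be judged unrelated.
- Infections and cardiovascular events: not named in that sentence of Section 8, so more likely to be filtered out when non-serious.

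The documents describe no separate reporting route for non-serious AEs judged unrelated.

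**Step 3: scale.** Input: n = 10 (Section 4.2). A patient is affected in a category if all of that patient's events in it are non-serious and judged unrelated.

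Loss in recorded incidence = affected patients / 10.

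- 0 patients: 0 / 10 = 0 points
- 1 patient: 1 / 10 = 10 points
- 2 patients: 2 / 10 = 20 points

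The number of affected patients is an assumption; the documents do not give it.

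**Step 4: illustration only.** Table 3-3 gives infections and infestations in 92 of 173 patients (53%). Let f be the share of patients with an infection who have at least one judged related; f is assumed. Expected patients recorded = 10 × 0.53 × f.

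- f = 100%: 5.3
- f = 75%: 3.98
- f = 50%: 2.65
- f = 25%: 1.33

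The table covers patients with cancer on combination regimens, so the 53% is not a forecast for this trial. The illustration shows that the loss ranges from nothing to large, depending on a quantity that the plan does not fix.

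**The case against.** The strongest reply is that this is one stray sentence. Section 8.1.1 and the end of Section 9.1 both point to unfiltered entry, and possibly related is a low bar. There are also safeguards: the DMC may review source documents (Section 9.1), monitors compare collected with electronic data for about 50–75% of subjects (Section 9.3), all CRF data go into the listings (Section 7.1.4), and Section 7.1.8 promises a data and safety monitoring plan covering AE reporting, which may settle the rule. All of this limits the harm. None of it says which rule governs, and a monitor cannot tell whether an unentered, unrelated AE is a discrepancy until one does.

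A reader might infer more than the documents support:

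- *That unrelated events are never collected.* Section 9.1 has the team ask about any events; the filter acts only at entry.
- *That cytopenias would be lost.* Section 8.1.1 enters laboratory AEs without a filter. A neutrophil or platelet count below the Section 6.3.1 limits delays the next cycle and so qualifies without any judgement of clinical significance. Laboratory results are also abstracted for study purposes (Section 9.1), so counts can be tabulated directly. One uncertainty remains: Section 9.1 says that the PI will not classify abstracted results as clinically significant or not, which may disable the last trigger in Section 8.1.1.
- *That the tested safety endpoint is biased.* Section 7.1 tests discontinuation due to AEs. Section 6.12 requires the primary withdrawal reason in the source documents and CRF, and Section 8.1.1 covers laboratory values that lead to discontinuation.
- *That the missing events would also be absent from the final report.* Section 9.4.2 provides for paper as well as electronic collection tools, so absence from OnCore does not establish absence from the CRF listings.

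**Conclusion.** The concern holds: the plan is wrong as written. Section 9.1 contains two entry rules for one database that cannot both be followed, and the related-only sentence also conflicts with Section 8.1.1 and with a primary safety list that is mostly free of any relatedness condition.

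The consequence is conditional. If the related-only sentence is followed, non-serious AEs judged unrelated drop out of the OnCore-based DMC reports, and recorded incidence can only go down. Each affected patient costs 10 percentage points in a category. How many patients would be affected cannot be derived from the documents, and the number may be zero. The conflict in the wording does not depend on that number.

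**What to change.** Delete the related-only sentence from the first paragraph of Section 9.1, so that Section 8.1.1 and the last paragraph of Section 9.1 govern. State that every AE is entered in OnCore, with relatedness to ixazomib and relatedness to dexamethasone as two data fields and not as conditions for entry. A related-only summary can then still be produced from the complete data, and the question of which drug the filter refers to no longer affects entry.

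In the same amendment, reconcile the statement in Section 9.1 that the PI makes no clinical-significance determinations on abstracted laboratory results with the trigger in Section 8.1.1 that relies on such a judgement. Carry the same entry rule into the data and safety monitoring plan.

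The cost is protocol wording and slightly more data entry for 10 patients. Tables 2-1(a) and (b) already schedule 13 AE assessments per patient after Day 1, so 13 × 10 = 130 at most. No visit or test is added.

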6.3 Dose-Modification Guidelines

The ixazomib dose reduction steps are 3 mg \rightarrow 2.3 mg \rightarrow 1.5 mg (Table 4-1), and the dose modification guidelines are provided in the IB and Table 4-2 and 4-3 below.

Treatment monitoring and dose modifying strategies. Liver Function Tests will be conducted twice a month for the first 3 months, then monthly thereafter. The Complete Blood Count (CBC) will be checked monthly. They will undergo clinical evaluation at baseline and every three months until the end of the study. Ixazomib dose modifying strategies will be implemented as outlined in the IB.

6.3.1 Recommended Ixazomib Criteria for Beginning or Delaying a Subsequent Treatment Cycle & Dose Modifications for Treatment Associated Toxicity

Treatment with ixazomib will use a cycle length of 28 days. For a new cycle of treatment to begin, the patient must meet the following criteria:

- ANC must be $\geq 1,000/\text{mm}^3$.
- Platelet count must be $\geq 75,000/\text{mm}^3$.
- All other nonhematologic toxicity (except for alopecia) must have resolved to \leq Grade 1 or to the patient's baseline condition

If the patient fails to meet the above-cited criteria for initiation of the next cycle of treatment, dosing should be delayed for 1 week. At the end of that time, the patient should be re-evaluated to determine whether the criteria have been met. If the patient continues to fail to meet the above-cited criteria, delay therapy and continue to re evaluate. The maximum delay before treatment should be discontinued will be 3 weeks or at the discretion of the Principal Investigator.

For dosing recommendations upon recovery, refer to Table 642 and Table 4-3.

Table 4-1 Ixazomib Dose Adjustments

| Dose Level | Dose (mg) |
|---------------|-----------|
| Starting Dose | 3.0 mg |

| | |
|-----------------------------|-------------|
| First Level Dose Reduction | 2.3 mg |
| Second Level Dose Reduction | 1.5 mg |
| Third Level Dose Reduction | Discontinue |

Once ixazomib is reduced for any toxicity, the dose may not be re-escalated.

Dosage adjustments for hematologic toxicity are outlined in Table 4-2.

Table 4-2 **Ixazomib** Dose Adjustments for Hematologic Toxicities

| Criteria | Action |
|---|--|
| Dose Modifications for Treatment Cycles | |

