7. STATISTICAL AND QUANTITATIVE ANALYSES

7.1 Statistical Methods

More than 50% of patients with CDC T cell crossmatch titers $\geq 1:8$ and/or cPRA $> 80\%$ fail to respond to desensitization (5, 8). In this pilot exploratory, proof of concept, open-label, single-center phase II clinical trial, we hypothesize that our study will have a higher rate of transplantation. [name], PhD, epidemiologist and biostatistician in the division of nephrology, will perform the statistical analyses. *Primary* efficacy (decline in cPRA $> 20\%$) and safety (discontinuation of therapy due to adverse events) endpoint will be analyzed using the exact binomial test. The *secondary* endpoint (time to transplantation) will be assessed using Kaplan-Meier analyses and log rank tests. Baseline characteristics will be compared between participants with and without the primary end point using the 2-sample t test for continuous variables and the Fisher's exact test for categorical variables. Relationships between serum BAFF/APRIL, antibodies, and baseline cPRA will be assessed using the Pearson correlation coefficient. The influence of serum BAFF/APRIL, antibodies, and bone marrow plasma cells on end points of interest will be investigated using Kaplan-Meier curves and Cox proportional-hazards models.

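### Section 9.1 withdraws the one judgement-based route in Section 8.1.1 by which a laboratory change becomes an adverse event, so cytopenias that prompt no action may go unrecorded

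*Combined protocol and SAP*

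**What the plan says.** Section 8.1.1 starts from the position that an abnormal laboratory value is not an AE, "unless that value leads to discontinuation or delay in treatment, dose modification, therapeutic intervention", or the value "is considered by the investigator to be a clinically significant change from baseline". That gives three kinds of action and one judgement.

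Section 9.1 says that "it is anticipated that the laboratory results that will be abstracted from the EMR for study purposes will be abnormal", and continues: "The PI will not make clinically significant/non-clinically significant determinations of these results, as this subject population is expected to be abnormal".

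Section 3.1 lists "hematological complications including leucopenia, anemia, and thrombocytopenia" in the primary safety endpoint. Section 7.1.8 repeats the list as a focus of the safety analysis, and Section 9.1 repeats it as data for the DMC. Section 7.1 describes the tested endpoint more narrowly: "safety (discontinuation of therapy due to adverse events) endpoint will be analyzed using the exact binomial test".

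**The concern.** Staff cannot follow both rules. If Section 9.1 governs, nobody is assigned the judgement that Section 8.1.1 relies on for a laboratory change that prompted no action. Section 9.1's other source of AEs is asking subjects about signs and symptoms, which will not reveal a cytopenia without symptoms.

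What is at stake is the completeness of a named part of the primary safety endpoint in a 10-patient trial. The DMC's reports are built from the OnCore system, where these AEs are entered, and Section 9.1 leaves the harm boundary to the DMC's judgement. No numerical stopping rule would compensate for an incomplete count.

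**Working it through.** There is no stated figure to reproduce; the check is mainly a comparison of texts.

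**Step 1. Which routes does Section 9.1 affect?**

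| Route in Section 8.1.1 | Needs a significance judgement? | After Section 9.1 |
|---|---|---|
| Discontinuation or delay | No | Open |
| Dose modification | No | Open |
| Therapeutic intervention | No | Open |
| Clinically significant change from baseline | Yes | Contradicted |

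**Step 2. Does the stated reason justify the bar?** Section 9.1 argues that results will be abnormal in this population. Section 8.1.1 asks about change from baseline. A patient who starts abnormal can still change, and Table 2-1(a) schedules a blood count on Day 1 to measure the change against. The reason therefore does not answer the test.

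**Step 3. Which cytopenias fall between the open routes?** The inputs are the cycle-start criteria in Section 6.3.1 (neutrophils at least 1,000/mm³, platelets at least 75,000/mm³), Table 4-2 (a delay of more than 2 weeks leads to a dose reduction), Section 6.5 (transfusion and growth factors permitted) and Section 5.1 (hemoglobin above 6 g/dL, for eligibility only).

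- *Thrombocytopenia.* A count below 75,000 at cycle start delays dosing and so becomes an AE. A fall that stays at or above 75,000 and prompts nothing does not.
- *Leucopenia.* It is captured through delay only if neutrophils are below 1,000. As an illustration, white cells of 1,800/mm³ with neutrophils of 1,050/mm³ pass the cycle-start criteria, although Section 8.1.2 classes white cells from 1,000 to below 2,000/mm³ as Grade 3.
- *Anemia.* The protocol text has no hemoglobin criterion for starting a cycle or changing dose. Anemia becomes an AE only if treatment is in fact held, changed or stopped, or if there is an intervention such as transfusion. It is the most exposed of the three.

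At the Day 373 visit the last dose has already been given, so delay and dose change cannot apply to that blood count. Only intervention or judgement remains.

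**Step 4. Rough size.** Expected total cases = 10 × the rate in Table 3-2 (single agent) or Table 3-3 (combination).

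| Term | Table 3-2 | Cases in 10 | Table 3-3 | Cases in 10 |
|---|---|---|---|---|
| Thrombocytopenia | 34% | 3.4 | 28% | 2.8 |
| Anemia | 21% | 2.1 | 26% | 2.6 |
| Neutropenia (stand-in for leucopenia, which neither table lists) | 14% | 1.4 | 25% | 2.5 |

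These are all cases, not missed cases. If *f* is the share that prompts no action, the number missed is *f* times the figure shown. The documents do not give *f*, so the loss ranges from 0 (*f* = 0) to the whole figure (*f* = 1). Each missed patient changes an observed rate by 1/10 = 10 percentage points.

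**The case against.** The strongest defence is that Section 9.1 hides little. Three of the four routes are untouched. Section 9.1 has monthly laboratory results reviewed before each dispensing, Section 7.1.4 puts all recorded data into listings, the DMC receives hematological complications by name and may see source documents, and the endpoint that Section 7.1 tests, discontinuation for AEs, uses an open route. All of this stands, and it limits the point to cytopenias without action. It does not remove the point: reviewing a result is not recording an event, and a listing of ungraded values is not a count of leucopenia, anemia or thrombocytopenia. Nothing in Section 7.1.8 says how blood counts are to be graded or summarised.

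A second defence concerns scope. Section 9.1 binds the principal investigator and results taken from the medical record, while Section 8.1.1 speaks of the investigator. The sentence may be meant only to avoid routine annotation of reports that are expected to be abnormal. That reading is plausible, but no section assigns the judgement to anyone else.

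Third, Section 6.3 also refers to the Investigator's Brochure for dose modification, and Section 7.1.8 to a monitoring plan still to be developed. Neither is among the documents reviewed. If either sets a white-cell or hemoglobin action limit, fewer cases would be lost.

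A reader might also argue that the eligibility limits disprove the premise of abnormal results. They do not: they admit platelets of 75,000/mm³, transaminases up to 3 times the upper limit of normal and hemoglobin just above 6 g/dL. The argument from change from baseline does not depend on them.

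**Conclusion.** The conflict between Sections 9.1 and 8.1.1 is real and should be resolved. Its consequence is possible under-recording, as AEs, of cytopenias that prompt no treatment action: anemia first, then low white cells with neutrophils at or above 1,000/mm³ and platelet falls that stay at or above 75,000/mm³.

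A reader might infer more, namely that Section 9.1 closes off laboratory AEs altogether and conceals the hematologic part of the primary safety endpoint. The documents do not support that, because any value leading to discontinuation, delay, dose change or intervention is still an AE.

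The number missed cannot be derived. The figures of about 3 thrombocytopenia, 2 to 3 anemia and 1 to 3 neutropenia cases in 10 are a rough indication of total cases. They come from oncology and amyloidosis patients on various doses, schedules and combinations, and applying them to kidney transplant candidates is an assumption. The conclusion also assumes that Section 9.1 is followed as written and that no action limit for hemoglobin or white cells applies from outside the protocol text.

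**What to change.** 1. Reconcile Sections 8.1.1 and 9.1. Either delete the Section 9.1 sentence that bars clinical-significance determinations, or limit it to values unchanged from baseline. Use the same role name in both sections.
2. In Section 7.1.8, define the hematologic safety summary from the scheduled blood counts: each patient's worst post-baseline CTCAE grade and the shift from Day 1, whatever the relatedness or action taken. CTCAE is already used in Sections 5.2 and 8.2.
3. Include this table in the DMC reports. It would not depend on which AEs reach OnCore, a matter on which Section 9.1 is itself inconsistent: one paragraph enters only related AEs, another all AEs and SAEs.

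The cost is an amendment to the wording and one table from data already scheduled for collection. More low-grade events will be reported; the shift from Day 1 separates them from abnormality present at baseline. No change to dosing or clinical management is proposed.
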